8.2.6 Treatment-Emergent SAEs that Led to Premature Discontinuation of Study

All treatment-emergent SAEs that led to subject discontinuation from the study will be summarized and listed separately.

8.2.7 Deaths

Deaths will be listed.

8.3 Clinical Laboratory Evaluations

Hematology, blood chemistry, and urinalysis parameters will be summarized at baseline and at each time point. Additionally, the change from baseline in each parameter will be summarized. Laboratory values and changes from baseline in laboratory values will be summarized descriptively by treatment group.

A summary of shifts from baseline will be given for each treatment group for each parameter. The normal range for each parameter will be used to create categories of low, normal, or high. Any result higher than upper limit of normal or lower than lower limit of normal will be categorized as high or low respectively, and any result within the lower and upper limits of normal will be categorized as normal. The number and percentage of subjects in each treatment group in each shift category from baseline to final evaluation will be shown for each parameter.

Hepatitis Panel data (Hep B surface antibody, Hep B Surface antigen, Hep B core antibody total, HCV antibody and hepatitis A virus (HAV) total) collected will be listed.

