1.3 Clinical Experience with SAN-300

A total of 66 healthy volunteer subjects and two patients with active RA participated in Phase 1 Study C2011-0301 (301), in which 45 healthy subjects and one patient with active RA received single doses of SAN-300 via IV infusion or SC injection. Detectable serum SAN-300 concentrations were not observed in the majority of subjects receiving SAN-300 0.03 mg/kg to 0.3 mg/kg IV. In subjects receiving SAN-300 0.6 to 2.0 mg/kg, there was a trend towards increasing serum SAN-300 concentrations with increasing dose. Receptor occupancy was essentially complete (\geq 90%) over a wide range of doses tested for both the IV and SC formulations (by 72 hours postdose for > 0.8 mg/kg IV and by 24 hours postdose for 2.0 to 6.0 mg/kg SC). Receptor occupancy was also durable, with median occupancy remaining at approximately \geq 70% at Day 8 for all dose groups administered SAN-300 SC.

Amendment 5: 28 Mar 2016

SAN-300 was generally well tolerated in this study. Mild to moderate infusion reactions occurred upon IV administration of SAN-300 doses from 0.8 to 2.0 mg/kg; all events improved with or without treatment by 72 hours and none led to withdrawal from the study. Among subjects receiving SC SAN-300 at doses ranging from 2.0 to 6.0 mg/kg, headaches and mild injection-site reactions were most common. No severe or serious infections were reported in any group. No clinically meaningful changes from baseline were observed after SAN-300 dosing for biochemistry parameters and for the majority of hematologic parameters tested. Transient, Grade I/II reductions from baseline in absolute neutrophil count (ANC) were observed in 12 subjects who received SAN-300. None of these cases were associated with concurrent infections, and all resolved. Two subjects tested positive for treatment-emergent anti-SAN-300 antibodies; no immunogenicity-related adverse events were observed in these subjects. The safety findings from this Phase 1 study support further development with the proposed multiple ascending dosing regimen in patients with RA.

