8.5 Clinical Laboratory Tests

8.5.1 Laboratory Parameters

Blood samples for clinical laboratory assessments will be collected according to the Schedule of Assessments provided in Appendix 2. Patients will be in a seated or in a supine position during blood collection. Safety and Screening laboratory tests will include those listed in Table 3 and will be performed at a central laboratory.

Santarus, Inc.
SAN-300 Clinical Trial Protocol: C2013-0302

Amendment 5: 28 Mar 2016

Table 3. List of Laboratory Tests

Hematology:

- Hematocrit (Hct)
- Hemoglobin (Hgb)
- Mean corpuscular hemoglobin (MCH)
- Mean corpuscular hemoglobin concentration (MCHC)
- Mean corpuscular volume (MCV)
- Platelet count
- Red blood cell (RBC) count
- White blood cell (WBC) count with differential (neutrophils, lymphocytes, monocytes, eosinophils, and basophils)

Urinalysis:

- Appearance
- Bilirubin
- Color
- Glucose
- Ketones
- Microscopic examination of sediment
- Nitrite
- Occult blood
- pH
- Protein
- Specific gravity
- Urobilinogen
- Urine human chorionic gonadotropin (hCG) (only for females of childbearing potential)

Additional Assessments:

- Serum Immunoglobulin
- Serum tryptase
- Histamine
- C-reactive protein (CRP)
- Erythrocyte sedimentation rate (ESR) (conducted at site)

Serum Chemistry:

- Albumin (ALB)
- Alkaline phosphatase (ALK-P)
- Alanine aminotransferase (ALT; SGPT)
- Aspartate aminotransferase (AST; SGOT)
- Blood urea nitrogen (BUN)
- Calcium (Ca)
- Carbon dioxide (CO₂)
- Chloride (CI)
- Creatinine
- Creatine kinase
- Gamma-glutamyl transferase (GGT)
- Globulin
- Glucose
- Lactate dehydrogenase (LDH)
- Phosphorus
- Potassium (K)
- Sodium (Na)
- Total bilirubin
- Direct bilirubin
- Total cholesterol
- Total protein
- Triglycerides
- Uric acid
- Serum hCG (only for females of childbearing potential)

Coagulation:

- Prothrombin time (PT)
- Activated partial thromboplastin time (aPTT)
- International normalized ratio (INR)

Serology:

- Hepatitis B surface antigen (HBsAg)
- Hepatitis C virus (HCV) antibodies
- Human immunodeficiency virus (HIV) antibodies
- QuantiFERON[®]-TB Gold test (QFT)

Amendment 5: 28 Mar 2016

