2 STUDY OBJECTIVES AND ENDPOINTS

2.1 Study objectives

2.1.1.1 Primary Objective

• To evaluate the safety and tolerability of repeat doses of SAN-300 in patients with active rheumatoid arthritis (RA).

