14.3.1.6	Summary of Treatment-Emergent Adverse Events by System Organ Class,
	Preferred Term, Maximum Intensity and Treatment Group – Safety Population
14.3.1.7	Summary of Treatment-Emergent Adverse Events related to Study Drug, System

Number	Title
	Organ Class, Preferred Term and Treatment Group – Safety Population
14.3.1.8	Listing of Deaths – Safety Population
14.3.2.1	Summary of Mean and Mean Change from Baseline in Hematology/Coagulation Results by Treatment Group – Safety Population
14.3.2.2	Summary of Mean and Mean Change from Baseline in Blood Chemistry Results by Treatment Group – Safety Population
14.3.2.3	Summary of Mean and Mean Change from Baseline in Urinalysis Results (pH and Specific Gravity) by Treatment Group – Safety Population
14.3.2.4	Summary of Urinalysis Results (Other Parameters) by Treatment Group – Safety Population
14.3.2.5	Summary of Shift from Baseline in Hematology/Coagulation Results by Treatment Group – Safety Population
14.3.2.6	Summary of Shift from Baseline in Chemistry Results by Treatment Group – Safety Population
14.3.2.7	Summary of Shift from Baseline in Urinalysis Results by Treatment Group – Safety Population
14.3.2.8	Summary of Post-Baseline CTC Grades Increase – Safety Population
14.3.2.9	Summary of Study Specific Laboratory Test Results by Treatment Group – Safety Population
14.3.3	Summary of Mean and Mean Change from Baseline in Vital Signs by Treatment Group – Safety Population
14.3.4	Summary of ECG parameters by Treatment Group – Safety Population

Listings

Number	Title
16.2.1	Subject Disposition – All Randomized Subjects
16.2.2	Analysis Population – All Randomized Subjects
16.2.3.1	Protocol Deviations – All Randomized Subjects
16.2.3.2	Inclusion and Exclusion Criteria – All Randomized Subjects
16.2.4.1	Demographic Characteristics and Informed Consent – All Randomized Subjects
16.2.4.2	Medical History – All Randomized Subjects
16.2.5.1	Drug Exposure Information – All Randomized Subjects
16.2.5.2	Methotrexate Initial Dosage - All Randomized Subjects
16.2.5.3.1	Prior and Concomitant Medications – All Randomized Subjects
16.2.5.3.2	Prior RA Treatments – All Randomized Subjects
16.2.5.3.3	History of Biologics – All Randomized Subjects
16.2.6.1	Disease Activity Score with 28-joint count using CRP (DAS28-CRP) Results – All Randomized Subjects
16.2.6.2	ACR Core Set Measurements Results – All Randomized Subjects

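### Laboratory shift tables compare baseline only with an undefined final evaluation, so a neutrophil fall that recovers by then counts as no shift, although other outputs still hold it

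*SAP*

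**What the plan says.** SAP 8.3 classifies each result as low, normal or high against the normal range. Counts and percentages per treatment group "in each shift category from baseline to final evaluation will be shown for each parameter". Appendix 2 carries this into Tables 14.3.2.5 to 14.3.2.7, the first titled "Summary of Shift from Baseline in Hematology/Coagulation Results by Treatment Group". No shift to a worst or lowest post-baseline value is specified.

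The SAP does not say which evaluation is final. SAP 4 defines an end-of-treatment value as the last available one in the treatment period, nominally Day 43. SAP 3.1 places the Exit Visit on Day 71. SAP 8.3 refers to neither.

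The shift is not the only laboratory output. SAP 8.3 also says: "Hematology, blood chemistry, and urinalysis parameters will be summarized at baseline and at each time point", with changes from baseline, and SAP 4 includes the minimum and maximum in every continuous summary. Appendix 2 adds a table of post-baseline CTC grade increases (14.3.2.8), a listing of all haematology results (16.2.8.1.1), a listing of haematology results of CTCAE Grade 1 or above (16.2.8.1.2), and a listing of results of Grade 3 or above or with a shift of at least 2 (16.2.8.6).

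Protocol 1.3 gives the background: "Transient, Grade I/II reductions from baseline in absolute neutrophil count (ANC) were observed in 12 subjects who received SAN-300", and "None of these cases were associated with concurrent infections, and all resolved". Neutrophils are measured in this trial as part of the differential (Protocol 8.5.1).

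**The concern.** The primary objective is "To evaluate the safety and tolerability of repeat doses of SAN-300". The haematology signal carried forward from Phase 1 is a fall in ANC that comes and goes, and ANC is the laboratory value named in the stopping rules (Protocol 3.4.1 and 3.4.2). A table that looks only at the last value suits a lasting change and is weak for a transient one. A patient who is normal at baseline, low during dosing and normal again at the final evaluation enters the normal-to-normal cell.

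The SAP takes the opposite approach for other safety data. ECG abnormalities are tabulated by the worst value during treatment (SAP 8.8), and adverse events by maximum intensity (SAP 8.2.2). No reason is given for treating laboratory shifts differently.

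What is at stake is the count, by arm and against pooled placebo, of patients whose neutrophils fell below normal at any time on study. The shift tables as defined do not give that count.

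**Working it through.** The plan states no figure on this point and has no sample size calculation, so there is nothing to reproduce. The check has three parts.

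**1. How much data the shift uses.** The schedules (Protocol Appendix 2, SAP Appendix 1) place post-baseline blood counts on Days 8, 15, 22, 29, 36, 43, 57 and 71, which is eight. The shift uses one. The interval from the last active dose to the final evaluation depends on the reading:

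| Final evaluation | After last weekly dose (Day 36) | After last every-other-week active dose (Day 29) |
|---|---|---|
| Day 43 | 43 − 36 = 7 days | 43 − 29 = 14 days |
| Day 71 | 71 − 36 = 35 days | 71 − 29 = 42 days |

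**2. Scale of the signal (an assumption, not a forecast).** Protocol 1.3 gives 12 subjects with a fall. For the denominator, "45 healthy subjects and one patient with active RA received single doses" of SAN-300, so 45 + 1 = 46.

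- Crude rate: 12/46 = 26.1%; Clopper-Pearson 95% CI 14.3% to 41.1%.
- Expected among the 30 planned active patients (Protocol 3.1): 30 × 0.261 = 7.8. At the limits, 30 × 0.143 = 4.3 and 30 × 0.411 = 12.3.
- Chance of at least one in an arm of 6: 1 − (1 − 0.261)^6 = 0.84. At the limits, 1 − (1 − 0.143)^6 = 0.60 and 1 − (1 − 0.411)^6 = 0.96.

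**3. What a baseline-to-final shift would show of those falls (illustration).** Assume that each fall goes below the lower limit of normal in a patient not low at baseline, that onset is equally likely at each of the six visits from Day 8 to Day 43, and that the fall lasts one, two or three consecutive scheduled visits. The share still low at the final evaluation, and that share of 7.8 falls, would be:

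| Duration | Final = Day 43 | Final = Day 71 |
|---|---|---|
| 1 visit | 1/6, about 1.3 | 0/6, 0 |
| 2 visits | 2/6, about 2.6 | 0/6, 0 |
| 3 visits | 3/6, about 3.9 | 1/6, about 1.3 |

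Under the same assumptions, a shift to the lowest post-baseline value would count all 7.8. So the shift table shows at most half of the falls on the Day 43 reading, and at most one sixth on the Day 71 reading.

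**The case against.** The strongest reply is that the signal stays in the report. With about six patients per arm, the by-visit minimum ANC shows the lowest patient in each arm at each visit, so it is not enough to say that means dilute single patients. Phase 1 reported the falls in grades, so a grade-increase table is arguably a better match than low/normal/high. The Grade 1-or-above listing would carry graded falls patient by patient. Clinically significant abnormalities that meet the definition are also recorded as adverse events (Protocol 9.2). All of this stands, and it rules out any claim that the falls would be lost.

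It does not fully close the gap. Table 14.3.2.8 exists only as a title: the SAP gives no grading version, parameter list or rule for which post-baseline value is graded. By-visit minima do not count patients across visits. Listings give patient lines, not counts by arm. Listing 16.2.8.6 would not pick up a one-grade fall to Grade 1.

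A reader might also infer that the final evaluation is Day 71 and that every fall will have resolved by then, so the shift table would show none. The documents do not support this. The term is undefined, and on the Day 43 reading a late fall could still be seen. Protocol 1.3 says that the falls resolved but not how quickly, and it describes single doses rather than six weeks of dosing.

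Nor can 26% be read as a drug effect. It pools IV and SC single doses, almost all in healthy volunteers, and no rate is given for the 22 participants (66 + 2 − 46) who did not receive SAN-300. The protocol does not say that the falls crossed the lower limit of normal, which is what the shift table counts.

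**Conclusion.** The point holds in a limited form. As defined, Tables 14.3.2.5 to 14.3.2.7 cannot show an abnormality that appears after baseline and resolves by the final evaluation, and which visit that is remains open. For a trial with safety as its primary objective and a transient ANC signal from Phase 1, this is a poor choice of categorical display and worth correcting. The defect is under-display by arm in one set of tables; nothing indicates that the falls would be missing from the safety reporting as a whole.

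The size cannot be fixed from the documents. The expected counts rest on carrying the crude Phase 1 rate over to repeat dosing in patients with RA. The share missed rests further on assumed onset, duration and crossing of the lower limit. Only the mechanism follows directly from the SAP text.

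**What to change.** In SAP 8.3:

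- Add a shift from baseline to worst post-baseline value, including unscheduled samples, for the Treatment Period and for the whole study. Do this at least for ANC and the other haematology parameters (Table 14.3.2.5). The ANC argument does not by itself require it for chemistry and urinalysis, though one rule for all three tables would be simpler.
- Keep the baseline-to-final shift as a second panel showing recovery, and define the final evaluation by visit or window. Say whether samples taken after withdrawal to follow an abnormality count (Protocol 7.2, SAP 9.1).
- State the grading version, the parameters and the worst-value rule for Table 14.3.2.8.

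The cost is a few lines of SAP text and some programming, with no new data. The downside is that worst-value tables show more abnormalities in every arm, including placebo, because each patient is judged on the most extreme of several samples. They must be read against the pooled placebo column.

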8.4 Other Laboratory Evaluations

Other laboratory parameters include anti-SAN-300 antibody levels, rheumatoid factor (RF), antinuclear antibody (ANA), and anti-citrunillated peptide antibodies (ACPA). All other laboratory parameters will be summarized using descriptive statistics and presented by time point and treatment group. All other laboratory parameters will be presented for individual patients in data listings.

8.5 Prior and Concomitant Medications

All prior medications and concomitant medications captured in the Electronic Data Capture system will be coded to preferred term using World Health Organization Drug (WHODRUG) dictionary (September 2015). Concomitant medications will be summarized by Anatomical Therapeutic Chemical (ATC) Class term and preferred term for the Safety population.

Medication start and end dates will be used to determine whether a medication is prior, concomitant or newly initiated. When start and end dates are incomplete or missing and the medication category cannot be determined, the standard Salix estimation rule for concomitant medications will be followed.

8.5.1 Prior Medications

Prior medications are defined as any medication ended prior to the first study drug administration. All prior medications captured in CRF will be summarized and listed.

8.5.2 Concomitant and Newly Initiated Medications

Concomitant medications (medications taken at any time after first dose date including those taken prior to and continued after first dose date) and newly initiated medications (medications taken after initiation of the study drug administration) will be listed by subject and tabulated overall and by treatment group. In this summary, the number and percentage of subjects who take at least one concomitant medication and the number and percent of subjects who take each specific concomitant medication will be presented by ATC class, preferred term, and treatment group.

8.6 Vital Sign Measurements

Vital sign measurements and change from baseline including body temperature, heart rate, sitting blood pressures, and weight will be summarized at each scheduled visit descriptively by treatment group.

8.7 Physical Exam

Physical examination data will be listed.

8.8 Electrocardiogram (ECG)

Actual value and change from baseline of ECG parameters will be summarized by treatment group using descriptive statistics. In order to assess the QT interval data, corrected QT values as

29

suggested in the FDA QTc Guidance Document will be calculated based on the following three methods.

- 1) Fridericia's correction: QTc=QT/RR^{0.33},
- 2) Bazett's Correction: QTc=QT/RR^{0.5},

And

3) Correction based on linear regression techniques: Based on the data from baseline study population, the intercept(a) and slope (b) will be estimated separately for males and females using the equation QT=a+b(1-RR). Those estimates will be used to calculate the corrected QT values at post baseline time points.

A summary table will be presented of the number and percentage of subjects with worst QTc, QRS, PR, and ventricular rate abnormalities observed during the treatment period. Specific criteria to be used include the following:

ECG Parameter	Definition
QT _c B interval	Absolute QT _c B interval prolongation values:
	$> 450 \text{ to} \le 480 \text{ msec}$
	$> 480 \text{ to} \le 500 \text{ msec}$
	> 500 msec;
	Increase from baseline values:
	$>$ 30 to \leq 60 msec
	> 60 msec;
QT _c F interval	Absolute QT _c F interval prolongation values:
	$> 450 \text{ to} \le 480 \text{ msec}$
	$> 480 \text{ to} \le 500 \text{ msec}$
	> 500 msec;

ECG Parameter	Definition
	Increase from baseline values:
	$> 30 \text{ to} \le 60 \text{ msec}$
	> 60 msec;
QRS duration	Absolute values are abnormally low \leq 50 msec, normal $>$ 50 to $<$ 120 msec, and abnormally high \geq 120 msec;
PR interval	Absolute values are normal $<$ 210 msec and abnormally high \ge 210 msec;
Ventricular rate	Absolute values are abnormally low \leq 50 bpm, normal $>$ 50 to $<$ 120 bpm, and abnormally high \geq 120 bpm.

9 STATISTICAL AND ANALYTICAL ISSUES

9.1 Handling of dropouts or missing data

Subjects who prematurely discontinue before the end of the treatment will be contacted via follow-up phone call as frequently as needed. If the patient is found to have an AE or clinically significant laboratory abnormality, the patient will be followed until the event/abnormality is resolved, or until the Investigator determines that further follow-up is no longer medically indicated.

For subjects who discontinue prematurely, the last completed post-baseline assessment will be used as EOT.

Missing data will not be imputed in other analyses unless specified otherwise.

For subjects who terminate early from the study, if the study day of the EOT visit falls into a specific protocol defined scheduled visit window, the EOT visit will be reassigned to that specific scheduled visit for the analyses by protocol defined scheduled visit.

For cases where the start date of an AE is not complete, the assumption is made that the AE is a treatment-emergent event unless there is evidence to the contrary.

For cases where the start or the stop date of medication is not complete, the assumption is made that the medication is a concomitant medication unless there is evidence to the contrary.

